6.11 Early Termination Visit

Any subject terminating from the study early during the treatment period will, at the time of withdrawal, be encouraged to complete all Visit 4 (Week 12) procedures if possible.

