5.6 Laboratory Parameters

A full clinical laboratory profile including hematology, biochemistry, lipids and other analyses will be performed during the study. Laboratory data will be transferred electronically by the Dynacare central lab. Blood samples are to be collected at Screening, Baseline, Week 6, Week 12 and at some unscheduled visits if it is necessary to repeat testing following abnormal laboratory results. Here is the list of the collected laboratory assessment:

Screening (Visit 1): The following screening laboratory assessments are to be performed during the screening period for the determination of study eligibility and the patient's current medical state at the time of study entry:

| | Determinations | |
|---|--|---|
| Hematology | RBC | |
| | Hemoglobin | |
| | Hematocrit | |
| | WBC | |
| | Platelet Count | |
| | Differential (to be performed only if WBC is abnormal) | Neutrophils Lymphocytes Monocytes Eosinophils Basophils |
| Biochemistry | AST | |
| | ALT | |
| | Bilirubin | |
| | Creatinine | |
| | eGFR | |
| Lipids | Triglycerides | |
| | Total cholesterol | |
| | LDL-Cholesterol | |
| | HDL-Cholesterol | |
| Urine (only for females of childbearing potential) | Human chorionic gonadotropin (hCG) urine pregnancy test | |

Baseline and Treatment Period (Visits 2, 3, and 4)

| Determinations | | |
|---|--|---|
| Hematology | RBC | |
| | Hemoglobin | |
| | Hematocrit | |
| | WBC | |
| | Platelet Count | |
| | Differential (to be performed only if WBC is abnormal) | Neutrophils Lymphocytes Monocytes Eosinophils Basophils |
| Biochemistry | AST | |
| | ALT | |
| | LDH | |
| | CPK | |
| | Creatinine | |
| | eGFR | |
| | Glucose (fasting) (at visit 2 and 4 only) | |
| | Insulin (fasting) (at visit 2 and 4 only) | |
| | HbA1c (at visit 2 and 4 only) | |
| | hs-CRP (at visit 2 and 4 only) | |
| Lipids / Other | Triglycerides | |
| | Total cholesterol | |
| | LDL-Cholesterol (direct-measured) | |
| | HDL-Cholesterol | |
| | VLDL Cholesterol | |
| | Apolipoprotein B (apo B) | |
| | Lipoprotein (a) [Lp(a)] | |
| | Non-HDL-C | |
| | small low-density lipoprotein (LDL) subclass particle concentration | |
| Urine (only for females of childbearing potential) | Human chorionic gonadotropin (hCG) urine pregnancy test (Visit 2 only) | |

Female patients of childbearing potential will have a urine pregnancy test performed at the Screening visit and at Baseline.

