6.2 Statistical Considerations

This is a randomized, parallel study with four treatment groups (placebo, beta-glucan 1.5 g, beta-glucan 3 g and beta-glucan 6 g). The statistical analysis will focus on the comparisons of the three active groups vs. placebo.

Descriptive statistics of all study variables will be presented overall and broken down by treatment group. Number of observations, mean, standard deviation, median, minimum and maximum will be presented for continuous variables. Count and proportion will be displayed for categorical variables.

Basic assumptions of the proposed analyses will be checked and data transformation or other analyses could be done if appropriate. For example, as some endpoints are likely to be skewed (ex. triglycerides, hsCRP), log-transformation might be used, in which case descriptive statistics would also include geometric means.

Laboratory parameters will be assigned to visits based on number of days from randomization and not based on scheduled visit at which the measurement was made. The time windows that will be used to assign measurements to visits are given in Appendix 2.

Values entered as less than a specified value will be considered as the specified value divided by 2 (e.g. entered value <0.2 will be analyzed as 0.1). Values entered as BLQ (Below Limit of Quantification) will be considered as the limit of quantification divided by 2. Values entered as more than a specified value will be considered as the specified value.

All statistical tests will be two-sided. Tests involving the comparisons of the active groups vs. placebo for the primary endpoint will be conducted at the 0.0167 significance level. All other tests will be considered secondary or exploratory and will be conducted at the 0.05 significance level.

No interim analysis on efficacy endpoints is planned for this study.

Statistical analyses will be done using SAS version 9.4 or higher.

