6.2.1 Handling of Missing Data

For efficacy laboratory endpoints, the screening value will be taken if the baseline value is missing.

In addition, the proposed statistical analysis will account for all available data and will not disregard subjects with missing data at either Week 6 or Week 12. However, in subjects who will only have a baseline measurement, the last observation carried forward approach will be used.

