6.4.2 Secondary Analysis

Secondary endpoints are expressed as change from Week 0 to Week 12. Those that are measured at baseline (Week 0), Week 6 and Week 12 will be analyzed as the primary endpoint, with the exception that tests will be conducted at the 0.05 significance level. Those measured at baseline (Week 0) and Week 12 only will be analyzed with an analysis of covariance (ANCOVA) model including treatment group and baseline value. Because it is expected that the distribution of hsCRP will be skewed, a log-transformation will be applied to hsCRP data prior to analysis. Geometric mean and geometric mean percent change will be added to the descriptive statistics that will be presented.

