9.2 Appendix 2 - Reporting windows for laboratory parameters

Number of days between a laboratory assessment and randomization will be calculated (date of assessment – date of randomization + 1 day), compared to the lab reporting window below, and the assessment will be assigned to the corresponding visit.

| VISIT | SCHEDULED VISIT | SCHEDULED DAY | SCHEDULED WINDOW (± DAYS) | SCHEDULED WINDOW (DAYS) | LAB REPORTING WINDOW (DAYS) |
|-------|--------------------------|---------------|-----------------------------------|-------------------------|-----------------------------|
| V1 | Screening | | Up to 7 days before randomization | <1 | <1 |
| V2 | Baseline (randomization) | 1 | | 1 | 1 to 2 |
| V3 | Week 6 | 42 | ±5 | 37 to 47 | 3 to 63 |
| V4 | Week 12 | 84 | ±5 | 79 to 89 | ≥64 |

Notes:

The algorithm chooses the mid-point between consecutive scheduled visits and so achieves that no gaps between reporting windows occur, and that reporting windows correspond to the schedule of assessments.

In cases where more than one non missing assessment falls within the same window, the closest assessment will be chosen.

The LAB reporting window for baseline visit include day 2 because some subjects were randomized on scheduled day 1 but laboratory parameters were taken only the next day, where day 2 is the day of first dose.

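### One laboratory window table covers hsCRP and HbA1c, which have no Week 6 visit, so an early-termination sample on days 43-63 is labelled Week 6 and left out of their only between-group analysis

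*SAP*

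**What the plan says.** **Visit assignment.** SAP 6.2 states: "Laboratory parameters will be assigned to visits based on number of days from randomization and not based on scheduled visit". No analyte is excepted. SAP Appendix 2 (9.2) holds one table: baseline days 1-2, Week 6 days 3-63, Week 12 day 64 or later. Its notes say "The algorithm chooses the mid-point between consecutive scheduled visits" and that "reporting windows correspond to the schedule of assessments".

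**Sampling.** The list in SAP 5.6 has "hs-CRP (at visit 2 and 4 only" and "HbA1c (at visit 2 and 4 only" (closing brackets omitted here). The schedule of visits (SAP Appendix 1, Protocol Appendix 2) agrees.

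**Analysis.** For secondary endpoints SAP 6.4.2 says: "Those measured at baseline (Week 0) and Week 12 only will be analyzed with an analysis of covariance (ANCOVA) model". The model contains treatment group and baseline value. SAP 6.4.3 has the same rule for exploratory endpoints. hsCRP falls under the first section and HbA1c under the second.

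**Early leavers.** Protocol 6.11 says that subjects who terminate during treatment will "be encouraged to complete all Visit 4 (Week 12) procedures if possible". Those procedures include hsCRP and HbA1c.

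**Missing data.** SAP 6.2.1 says that the analysis draws on every available value and keeps subjects who lack Week 6 or Week 12 data. It adds that "in subjects who will only have a baseline measurement, the last observation carried forward approach will be used".

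**The concern.** The windows suit analytes measured at three visits. For an analyte measured at two, they create a Week 6 slot that no planned test reads. SAP 6.2 also rules out falling back on the nominal visit label. A sample taken under Visit 4 procedures at an early exit on, say, day 60 therefore goes into that slot and drops out of the ANCOVA.

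At stake is the use of measured post-baseline data on one secondary and one exploratory endpoint, in subjects who left early. The early-termination visit exists to collect such data. If the rule stays open, someone must decide during programming or after unblinding what to do with these values.

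**Working it through.** **1. Reproduce the plan's cut.** The scheduled days in Appendix 2 are 1, 42 and 84. The mid-point of Week 6 and Week 12 is (42 + 84)/2 = 63, which matches the 63/64 cut exactly. The lower edge of Week 6 is not a mid-point: (1 + 42)/2 = 21.5, but the table starts at day 3 because baseline is held to days 1-2.

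**2. Apply the same logic to a two-visit analyte.** For hsCRP and HbA1c the consecutive scheduled samples are on days 1 and 84. (1 + 84)/2 = 42.5, so Week 12 would start on day 43. Days 43-63, which is 63 - 43 + 1 = 21 days, change label.

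**3. Follow one value through the plan.** Take hsCRP on day 1 and at an early-termination visit on day 60.
- Appendix 2 labels day 60 as Week 6.
- The SAP 6.4.2 ANCOVA needs a Week 12 change, and the subject has none.
- The value stays in Listing 7 and possibly in a Week 6 row of the biochemistry summary (SAP 6.5.6).

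**4. Does carry-forward recover it?** SAP 6.2.1 does not say whether having only a baseline measurement is judged per subject or per analyte. Compare two subjects who both attended Visit 3 and both left on day 60, one with an exit sample and one without:

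| Reading of SAP 6.2.1 | With exit hsCRP | Without exit hsCRP |
|---|---|---|
| Per subject (both have Week 6 lipids) | dropped | dropped |
| Per analyte, any later value counts | dropped | kept at zero change |
| Per analyte, only usable values count | set to zero change | set to zero change |

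The measured day-60 value is used on none of the three.

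**5. Size.** SAP 6.1 randomizes 264 to retain 240, an allowance of 264 - 240 = 24 (about 9%). The documents give neither the timing of withdrawal nor the share f who provide an exit sample. Assume even timing over 84 days:
- Days 43-63: 24 x f x 21/84 = 6f, which is 1.5 at f = 25%, 3 at 50% and 6 at 100%. The last is 6/264 = 2.3% of subjects.
- Days 3-63 (61 days), all labelled Week 6: 24 x f x 61/84, which is about 4.4, 8.7 and 17.4.

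**6. Primary endpoint.** The LDL-C model has a Week 6 term. A subject who leaves on day 60 still contributes through it, with the exit value or with the Visit 3 value if that is the one chosen within the window.

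**The case against.** **The table may not break its own rule.** Appendix 2 speaks of consecutive scheduled visits, not of visits per analyte, and the trial's visits are days 1, 42 and 84. A reader might infer that the SAP contradicts itself. The text does not go that far: the per-analyte cut of 42.5 is an extension, supported by the note on the schedule of assessments but not required by it. This stands. It does not alter the fact that the value goes unused.

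**The bias claim rests on one reading.** It is tempting to say that the plan drops leavers who were measured and keeps unmeasured ones as unchanged. In the comparison above, only one of three readings of SAP 6.2.1 gives that contrast, and the documents do not choose among them.

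**Exit samples may be rare.** Protocol 6.11 only encourages them. Subjects who stop product but remain in the study keep to scheduled visits (Protocol 4.3 and 5.5), and the scheduled Week 12 window is days 79-89. The 24 are an allowance for loss to follow-up, a group unlikely to give an exit sample. Six is therefore a ceiling under even timing.

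**A mid-treatment value is not a Week 12 value.** Leaving it out is a defensible choice. But the table already accepts day 64, which is 20 days before day 84, and SAP 6.2.1 commits to all available data. Day 43 is 41 days early, so the repair does stretch the window. Days 43-47 also lie inside the scheduled Week 6 window of days 37-47. The existing rule of taking the closest assessment would protect a true Week 12 value if both existed.

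**Conclusion.** The point holds as a narrow one. A stated rule keeps measured hsCRP and HbA1c values from early-termination visits on days 43-63 out of the only planned between-group analysis of those endpoints, against the SAP's commitment to use all available data. The values are not erased, since they remain in the listing.

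The expected number is about 1.5 to 6 subjects across four groups, given 24 leavers, even leaving times and 25% to 100% giving an exit sample. All three are assumptions for sizing, and a lower sampling share would give fewer. Any effect on the estimates should be small. The documents do not support a claim of systematic bias between measured and unmeasured leavers, or of any such loss in the primary LDL-C analysis. This is a worthwhile tidy-up and does not threaten the trial's main conclusion.

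**What to change.** Before unblinding, amend SAP Appendix 2 and 6.2.1:

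- Add a window row for analytes scheduled only at Weeks 0 and 12: baseline days 1-2, Week 12 from day 43. Use it for the hsCRP ANCOVA (6.4.2) and the HbA1c ANCOVA (6.4.3). Fasting glucose and insulin share the schedule but have no planned test, so for them it would affect only the descriptive tables.
- State that samples of these analytes on days 3-42 are listed only.
- State in 6.2.1 whether carry-forward is judged per subject or per analyte, and whether it applies to subjects whose only later sample falls on days 3-42.

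The cost is one table row, two sentences and a conditional line in the visit-assignment program. There are two downsides. A few values from about weeks 6 to 9 would count as Week 12, and lipids and hsCRP from the same draw could carry different visit labels. The row recovers only days 43-63. At full sampling that is about 6 of the roughly 17 exit samples now labelled Week 6; the rest stay out of the ANCOVA, but by a stated rule.

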7.3.1 Follow-up of Abnormal Laboratory Test Values

In the event of medically significant unexplained abnormal laboratory test values, the tests should be repeated and followed up until they have returned to the normal range and/or an adequate explanation of the abnormality is found. If a clear explanation is established, it should be recorded on the eCRF.

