6.5.6 Laboratory Parameters

Laboratory parameters, more specifically hematology and biochemistry parameters, will be summarized using descriptive statistics and presented by study visit (Screening, Baseline, Week 6 and Week 12) and treatment group.

All laboratory results will be listed.

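### The closest-value rule can leave abnormal or withdrawal laboratory values out of the only safety laboratory tables, and the SAP plans no worst-value or out-of-range table

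*SAP*

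**What the plan says.** SAP 6.2 sets the assignment rule for all laboratory data: "Laboratory parameters will be assigned to visits based on number of days from randomization and not based on scheduled visit". Appendix 2 of the SAP gives the windows. Week 6 has scheduled day 42, visit window days 37 to 47 and reporting window days 3 to 63. Week 12 has scheduled day 84, visit window days 79 to 89 and a reporting window from day 64 with no upper limit. Within a window, "In cases where more than one non missing assessment falls within the same window, the closest assessment will be chosen". No reference day and no tie rule are given.

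SAP 5.6 counts unscheduled repeats after abnormal results among the laboratory data. Protocol 7.3.1 says that for medically significant, unexplained abnormal values "the tests should be repeated and followed up until they have returned to the normal range", with an adequate explanation as the other possible end point. Under Protocol 6.11, a subject who leaves the study early will "be encouraged to complete all Visit 4 (Week 12) procedures if possible".

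SAP 6.5.6 says that hematology and biochemistry results "will be summarized using descriptive statistics and presented by study visit (Screening, Baseline, Week 6 and Week 12) and treatment group". These are Tables 3.6.1 and 3.6.2. All results also go into Listing 7. SAP section 7 contains no worst-value, shift or out-of-range table.

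**The concern.** For a by-visit mean of an efficacy endpoint, taking the value nearest the scheduled day is a reasonable convention. For safety laboratory data it can work against the purpose of the table. A repeat is drawn because a value was abnormal, so whether a competing sample exists depends on the result. If the repeat is normal and nearer the scheduled day, the table shows the resolved value. A sample taken when a subject leaves the study can lose to a routine Week 6 sample taken before it.

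Hematology, AST, ALT, creatinine, LDH and CPK are scheduled at only two post-baseline visits, and safety is a stated secondary objective. At stake is whether the group summaries of these tests show the values a safety reader most wants to see.

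**Working it through.** **Inputs.** Scheduled days, visit windows and reporting windows are from SAP Appendix 2. Closest is taken as closest to the scheduled day, which is an assumption.

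**The plan's own figures.** Appendix 2 explains its windows thus: "The algorithm chooses the mid-point between consecutive scheduled visits". The boundary reproduces: (42 + 84)/2 = 63, so Week 6 ends on day 63 and Week 12 starts on day 64. The visit windows also reproduce: 42 ± 5 = 37 to 47 and 84 ± 5 = 79 to 89. The lower bound of Week 6 does not: (1 + 42)/2 = 21.5, against day 3 in the table. That mismatch plays no part below.

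**Repeat against the sample that triggered it.** Let the first sample fall k days before day 42 and the repeat r days after the first sample. The repeat is kept when |r − k| < k, that is, when r < 2k. A first sample on or after day 42 is never displaced by a later repeat. The largest k inside the visit window is 5 (day 37), so r is at most 9.

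| Repeat, days later | First-sample days displaced | Of 11 permitted days |
|---|---|---|
| 1 | 37-41 | 5 |
| 3 | 37-40 | 4 |
| 5 | 37-39 | 3 |
| 7 | 37-38 | 2 |
| 9 | 37 | 1 |
| 10 or more | none | 0 |

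For example, a raised value on day 38 is 4 days from day 42 and a normal repeat on day 44 is 2 days from it, so the repeat is tabulated. Week 12 behaves the same way on days 79-83: a value on day 80 (distance 4) loses to a repeat on day 86 (distance 2).

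Over repeats 1 to 14 days later there are 11 × 14 = 154 day-pairs per visit. Displacement occurs in 1 + 3 + 5 + 7 + 9 = 25 of them, and 5 are ties that the SAP does not resolve.

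**Sensitivity to the anchor.** Appendix 2 counts randomization as day 1, so exactly 6 and 12 weeks later are days 43 and 85. With those anchors the counts are 36 displaced and 6 tied, and the longest displacing interval is 11 days.

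**Early-termination sample.** Let Visit 3 fall k days from day 42, on either side. A later sample by day 63 is in the same window and loses when it is more than k days from day 42, that is, from day 42 + k + 1 to day 63, which is 21 − k days.

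| Visit 3 day | Withdrawal days on which the sample is lost | Number of days |
|---|---|---|
| 42 | 43-63 | 21 |
| 40 or 44 | 45-63 | 19 |
| 37 or 47 | 48-63 | 16 |

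Such a subject has no Week 12 sample, so the withdrawal value enters neither table. A withdrawal sample from day 3 onward but before Visit 3 is kept and labelled Week 6; from day 64 it is kept and labelled Week 12. The loss concerns tests also drawn at Visit 3. Glucose and insulin are not drawn there, so their withdrawal values have no competitor.

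**The case against.** A reader might infer that these results vanish from every safety table. The documents do not support that. Protocol 7.3 requires a clinically significant abnormal result (symptoms, a change in study product, or a change in concomitant therapy) to go on the adverse event page. SAP 6.5.2.1 tabulates treatment-emergent events, including those leading to withdrawal of the product, and Table 3.1.2 summarizes discontinuations. What is lost is the numeric value in Tables 3.6.1 and 3.6.2, and Listing 7 still holds it.

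Other limits also stand:

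- Protocol 7.3.1 covers unexplained values only, and follow-up may end with an explanation.
- Subjects who stop the product but stay in the study keep their visits (Protocol 4.3 and 5.5), so the withdrawal case needs someone who leaves altogether and gives the sample.
- Safety analysis is descriptive, and nearest-in-window selection is a deliberate, prespecified choice.

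The adverse event route is not a full backstop. Out-of-range results short of clinical significance are outside it. Protocol 6.9 and 7.4 collect non-serious events only up to the last dose, so an abnormality first seen in a sample drawn after stopping may not be recorded. Listing 7 gives no comparison by group.

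**Conclusion.** The point holds in a limited form and is worth acting on. Followed as written, the rule leaves result-dependent gaps in the only planned laboratory summaries. The gaps arise when the first sample precedes the scheduled day and the repeat is nearer to it, or when a subject leaves the study between Visit 3 and day 63.

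The table list also leaves a protocol commitment unmet. Protocol 7.3 says that out-of-range results that are not clinically significant are to be analysed and reported as such. SAP section 7 has no table for them, and SAP section 1 lets the SAP override the protocol where they differ.

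The size is given in days, not in probabilities. The fractions presuppose an abnormal value and a repeat, and they become rates only if visits fall evenly over the window. The documents give no frequency of repeats or withdrawals. A reader might go further and conclude that group means are biased towards no effect. That direction is plausible when repeats are normal, but nothing in the documents allows its size to be estimated, so it should not be claimed. All counts rest on day 42 or day 84 as the anchor.

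**What to change.** Before unblinding, amend the SAP as follows:

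1. Keep the closest-value rule for efficacy endpoints and by-visit means, and state its anchor day and tie rule.
2. Add one table by treatment group of the worst post-baseline hematology and biochemistry value per subject, with counts below and above the reference range against baseline. Build it from all scheduled, unscheduled and early-termination samples up to a stated number of days after the last dose.

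Two further changes are optional: using the scheduled-visit sample in the by-visit safety tables, and giving early-termination samples their own column.

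The cost is SAP wording, one table and a little more programming. No new data are needed, because the results are already part of the central laboratory transfer.
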